¹ **Undue influence**, often occurs through an offer of an excessive or inappropriate reward or other overture in order to obtain compliance. For example, an investigator might promise psychology students extra credit if they participate in the research. If that is the only way a student can earn extra credit, then the investigator is unduly influencing potential subjects. If, however, she offers comparable non-research alternatives for earning extra credit, the possibility of undue influence is minimized.

4. *To whom payment will be made (subject, parent [which one], legally authorized representative):*
5. *Payment schedule:*
 - a. *When payment will occur:*
 - b. *The payment schedule (amount at each time point), including details about the payment schedule and amount for subjects who withdraw or are withdrawn from the study:*

D.4.4 Reimbursement

Will subjects be reimbursed for their expenses, such as travel, parking, meals, or any other study related costs?

Yes No Yes No

E. Costs to Subjects

Does the research involve any costs to subjects?

Yes No Yes No

F. Study Design

F.1 Study Timelines

1. *Describe the duration of an individual subject's participation in the study:* one day, maximum 2 hours participation
2. *Describe the duration anticipated to enroll all study subjects at the Tufts study site:* 1 year
3. *Describe the estimated date for investigators to complete this study (complete primary analyses):* December 2019
4. *Describe the study procedures that will be accomplished at each study visit:* At each study visit, subjects in cohorts A, B, and C will undergo a whole-body DXA scan and all subjects will undergo an A-mode ultrasound at 7 anatomical landmarks on the dominant side, using the BodyMetrix Pro ultrasound (Intelametrix, Brentwood, CA).

F.2 Procedures

1. Is there a placebo control arm?
 Yes No Yes No
2. *Provide a description of all research procedures being performed as follows:*
 - a. *How individuals will be screened for eligibility. Specify screening that will take place prior to informed consent and screening that will take place after informed consent:*
 - Cohort A: Healthy volunteers (who may be employees)
 - Potential participants will be asked to confirm age >18 and no history of heart failure
 - Arrangements will be made for a urinary pregnancy test if there is a possibility of pregnancy

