- 1) Any experience when, based upon medical judgment, it may jeopardize the patient or subject and may require medical or surgical intervention to prevent one of the outcomes listed in this definition

H.2 Reporting Procedures

1. Describe the protocol-specific reporting procedures, including who will be responsible for each step (e.g., PI, Data Coordinating Center, Medical Monitor), which forms should be completed, timeframes for reporting, how reports will be distributed, and what follow-up is required: Any events, although not anticipated, will be reported to the IRB.
2. Include specific details of reporting procedures for:
 - a. Deaths, life-threatening events, pregnancies: Any events, although not anticipated, will be reported to the IRB.
 - b. Other SAEs: Any events, although not anticipated, will be reported to the IRB.
 - c. Other AEs: Any events, although not anticipated, will be reported to the IRB.
 - d. Other UPs: Any events, although not anticipated, will be reported to the IRB.

Ensure that the reporting procedures meet the reporting requirements of the FDA, NIH, OHRP, sponsor, study leadership and any other regulatory body that applies to the study, as applicable.

H.3 Reportable New Information

Check to confirm that reportable new information will be reported to the IRB per the Tufts Health Sciences IRB's [Reportable New Information policy](#). If your reporting plan to the IRB differs from the IRB's policies, please describe it in detail or specify where this information is in the protocol:

I. Statistical Considerations

I.1 Study Endpoints

1. Describe the primary and secondary study endpoints:

Primary DXA endpoint: fat free mass (FFM) measured by DXA

Primary ultrasound endpoint: FFM measured by BodyMetrix ultrasound

2. Describe any primary or secondary safety endpoints: N/A

I.2 Statistical Analysis

1. Describe the statistical analyses that will be performed for this study: Bland-Altman plot with bias and precision statistics to define the limits of agreement for FFM measured by DXA and ultrasound techniques.
2. Provide a power analysis: We previously showed good correlation between DXA and deuterium methods of FFM measurement in 8 patients with HF. Therefore we are aiming for a minimum enrollment of 60 subjects (10 per cohorts A-C, 30 per cohort D) and a maximum of 90 subjects total.

I.3 Number of Subjects

1. Specify the number of subjects to be enrolled in total across all sites: 90 or N/A this is not a multicenter study.

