2. Specify the number of subjects to be enrolled at the Tufts site. Subjects who sign an ICF are considered "enrolled". For studies that have a separate screening ICF, this number is the number of subjects who sign a screening ICF: 90
 - a. Provide the rationale for enrolling this number of subjects at the Tufts site: We plan to recruit a minimum of 60 subjects (10 per subgroups A-C, 30 per subgroup D) and a maximum of 90 subjects total.
 - b. Estimate the number of subjects expected to be enrolled at the Tufts site (i.e. sign the screening or study ICF) as well as the number needed to complete the study at the Tufts site: 90
 - c. If a large number of withdrawals and/or dropouts is expected, explain why: N/A

I.4 Data Management

1. Describe the data analysis plan, including descriptions of the data: Bland-Altman plot with bias and precision statistics to define the limits of agreement for FFM measured by DXA and ultrasound techniques. For skeletal muscle ultrasound to be considered a valuable technique for assessment of cachexia/sarcopenia, we would require the mean differences between the US and DXA measurement methods to be less than +/- 3, which is in line with our validation of DXA measurement of fat-free mass using the deuterium reference technique.
2. Provide a power analysis: See above
3. Describe the steps that will be taken to secure the data (e.g., training, authorization of access, password protection, encryption, physical controls, certificates of confidentiality, and separation of identifiers and data) during storage, use, and transmission: The data will be stored only on Tufts MC networked folders with password protection and accessed within accessed-controlled academic hospital areas.
4. Describe any procedures that will be used for quality control of collected data: Review of data by PI
5. Describe how data and specimens will be handled study-wide as follows:
 - a. What information will be included in that data or associated with the specimens: Subject number, sex, age, weight, body mass index, heart failure status.
 - b. Where and how data or specimens will be stored: N/A
 - c. How long the data or specimens will be stored: N/A
 - d. Specify who will have access to the data or specimens: Research team members only
 - e. Specify who is responsible for receipt or transmission of the data or specimens: N/A
 - f. Specify how data and specimens will be transported: N/A

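### The plan's one numeric requirement for ultrasound is set on the observed mean US-DXA difference and takes no account of its sampling error

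*Combined protocol and SAP*

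**What the plan says.** The primary objective (section C) is to validate ultrasound muscle measurement. Section I.1 names FFM by DXA and FFM by ultrasound as the endpoints ("Primary ultrasound endpoint: FFM measured by BodyMetrix ultrasound").

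Section I.2 item 1 plans the analysis as a "Bland-Altman plot with bias and precision statistics to define the limits of agreement for FFM measured by DXA and ultrasound techniques". Section I.4 item 1 repeats this and adds the only number: for ultrasound to be considered valuable, "we would require the mean differences between the US and DXA measurement methods to be less than +/- 3". The 3 has no unit. Its origin is described only by reference to the team's earlier work: "which is in line with our validation of DXA measurement of fat-free mass using the deuterium reference technique". The hypothesis in B.1 item 3 speaks of adequate agreement and attaches no figure. No section gives a confidence interval for the bias, an equivalence test or a significance level.

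On numbers, I.2 item 2 states a "minimum enrollment of 60 subjects (10 per cohorts A-C, 30 per cohort D) and a maximum of 90 subjects total". Its stated basis is: "We previously showed good correlation between DXA and deuterium methods of FFM measurement in 8 patients with HF". Under F.1 item 4, "subjects in cohorts A, B, and C will undergo a whole-body DXA scan and all subjects will undergo an A-mode ultrasound", so cohort D is not scheduled for DXA.

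**The concern.** An observed mean inside a limit does not show that the true bias is inside it. A mean of 2.9 with an interval reaching 4 would meet the requirement as worded, although the data would be compatible with a bias well beyond 3. The bias and precision statistics will be reported, but the requirement does not use them.

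When the true bias lies beyond the limit, noisier data also make it easier to land inside by chance. This matters because few pairs are planned and no SD or target precision supports their number. At stake is a statement that ultrasound meets the team's own standard and can be used in its later heart failure studies, with no stated control of the chance that the statement is wrong.

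**Working it through.** **The plan's own figure.** The minimum of 60 is 3 x 10 + 30. It cannot be reproduced as a power or precision calculation, because no SD, significance level, power or interval width is given.

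**Inputs**
- Limit: 3 (I.4 item 1). Kilograms are assumed because the endpoint is FFM.
- Pairs: cohorts A to C have DXA (F.1 item 4), so minimum enrollment gives n = 3 x 10 = 30, pooled. Leaving out the healthy volunteers gives n = 20.
- SD of the paired differences: not in the documents. Assumed to be 3 to 6 kg, with 4 kg as a middle value.

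**Requirement as written.** For true bias b, SE = SD/√n and P(met) = Φ((3 − b)/SE) − Φ((−3 − b)/SE). At SD 4 and n = 30, SE = 4/√30 = 0.73. At b = 3.5, (3 − 3.5)/0.73 = −0.685, so P = 25%. The second term is negligible. In the same way:

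| n = 30 | SE | b = 3.5 | b = 4 |
|---|---|---|---|
| SD 3 | 0.55 | 18% | 3% |
| SD 4 | 0.73 | 25% | 8.5% |
| SD 6 | 1.10 | 32% | 18% |

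With the 20 patient pairs and SD 6, SE = 6/√20 = 1.34 and the chances are 35% at b = 3.5 and 23% at b = 4.

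**Interval rule.** The requirement is met only if mean ± t × s/√n lies wholly inside ±3, where t is the 95th percentile of t with n − 1 degrees of freedom (1.699 at n = 30). This equals two one-sided 5% tests. Results are by simulation, with a normal mean and a chi-square variance.

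| True bias | n = 30, SD 4: as written | n = 30, SD 4: interval | n = 30, SD 6: interval | n = 20, SD 6: interval |
|---|---|---|---|---|
| 0 | >99% | 98% | 70% | about 40% |
| 1 | >99% | 85% | 53% | 31% |
| 2 | 91% | 38% | 22% | 15% |
| 3 | 50% | 5% | 5% | 5% |
| 3.5 | 25% | 1% | 2% | 2% |

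At n = 30, if the sample SD is 4, the half-width is 1.699 × 0.73 = 1.24, so the observed mean must lie within about ±1.76. If the sample SD is 6, the half-width is 1.86 and the bound is about ±1.14.

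**The case against.** The strongest case on the other side has five parts.

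- **A requirement is not a complete decision procedure.** I.4 says what the team would require. It does not say that meeting this is enough, and the bias and limits of agreement will be reported too. This stands: the percentages above are pass rates for one stated requirement, not for a full accept-or-reject verdict.
- **The study generates preliminary data** (B.1 item 2), and the documents do not use the word equivalence or plan a formal test. This lowers the severity. It does not remove the point, because the documents also speak of validating the method and of deploying it in later studies, and they chose a numeric limit for that purpose.
- **A reader might infer that a biased device is accepted half the time.** The documents do not support that as a general statement. The 50% arises only when the true bias sits exactly at the limit, is shared by any threshold on a point estimate, and assumes pooling. I.4 uses the plural for the mean differences. If each of three DXA cohorts had to pass, the chance at a true bias of 3 would be about 0.5³ = 12.5%.
- **Precision statistics could include an interval.** Possibly, but they are tied to defining the limits of agreement, and the requirement does not refer to them.
- **The interval rule can fail an unbiased device.** This is true and must be counted. At SD 6 with 20 pairs, it does so about 60% of the time.

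**Conclusion.** The point holds, as something that should be fixed rather than a fatal flaw. The structural part is certain: the only numeric requirement is on a point estimate, and no section asks how precisely the bias is known.

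The size is conditional. A pass rate of 18 to 32% at a true bias of 3.5 kg, and of 3 to 18% at 4 kg, rests on 30 pooled pairs, an assumed unit of kilograms and an assumed SD of 3 to 6 kg. More DXA pairs would lower these rates. At 60 pairs, if all 30 extra subjects joined cohorts A to C, the rates at 3.5 kg would be 10 to 26%.

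A reader might also infer that an interval on the mean would settle whether ultrasound agrees with DXA in individual patients. It would not. At SD 6 the limits of agreement would span about ±11.8 kg (1.96 × 6) even with zero bias. That is a separate question, which this point leaves open.

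**What to change.** In I.4 item 1, state three things:

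1. The requirement is met only if the 90% t-based confidence interval for the mean US-DXA difference lies wholly within -3 to +3, with the unit given.
2. A mean inside the limit whose interval crosses it is reported as inconclusive.
3. Whether the rule applies to the DXA cohorts pooled or to each one.

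In I.2 item 1, report the mean difference and each conventional limit of agreement with 95% confidence intervals. At 30 pairs each limit's interval is about ±0.645 SD (t × √(1/30 + 1.96²/58), with t the 97.5th percentile on 29 degrees of freedom), or ±2.6 kg at SD 4.

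The change is a few sentences and needs no new data, but the rule is harder to meet. At 30 pairs and SD 4, a device with a true bias of 2 kg would pass 38% of the time instead of about 91%. An unbiased device would pass about 70% of the time at SD 6, and about 40% if only 20 pairs were used. The team should accept in advance that an inconclusive result is possible, or plan more DXA pairs within the maximum of 90.
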